### Confidential

Page 17 of 27

Page 69 of 129

### 5.4.2 Adverse Events of Special Interest

Adverse events of special interest (AESI) will be identified based on a pre-defined list of preferred terms provided by the sponsor (Appendix 2).

AESI will be presented in a listing and summarized by SOC, PT and previous treatment group in parent study and overall in OLE study. A separate table for treatment emergent AESI resulting in the discontinuation of study drug will be summarized by SOC, PT, and previous treatment group in the parent study and overall in OLE study.

In addition to adverse events, AESI is also being evaluated based on safety lab parameters. The details are provided in 5.4.5.

## 5.4.3 Clinical Cardiovascular Endpoints

Clinical cardiovascular endpoints will be monitored and adjudicated by an independent blinded expert CEC for this study and other ongoing studies the ETC-1002 program. Adjudicated clinical endpoints that are treatment-emergent will be summarized by event type and previous treatment group in parent study and overall in OLE study. All events will be provided in a listing. Additional details regarding clinical endpoints and clinical endpoint definitions will be included in CEC charter.

### 5.4.4 Neurocognitive Events

Neurocognitive events will be identified and evaluated by routine safety monitoring of PE findings and AEs. Summarization of neurocognitive events will occur using pre-specified MedDRA terms and will be performed by SOC, severity, and relationship to study drug by previous treatment group in parent study and overall in OLE study.

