11.1.3. Reporting for Adverse Events

All AEs occurring during the course of the study (starting from signing informed consent through 30 days after last dose of bempedoic acid) will be collected on the AE eCRF. Patients should be instructed to report any AE that they experience to the investigator. Investigators should make an assessment for AEs at each visit and record the event on the appropriate AE eCRF.

Wherever possible, a specific disease or syndrome rather than individual associated signs and symptoms should be identified by the investigator and recorded on the eCRF. A cluster of signs and symptoms that results from a single cause should be reported as a single AE (eg, fever,

Bempedoic Acid Clinical Study Protocol 1002-050

elevated white blood cells [WBC], cough, abnormal chest X-ray, etc, can all be reported as "pneumonia" if that is the final diagnosis). However, if an observed or reported sign or symptom is not considered a component of a specific disease or syndrome by the investigator, it should be recorded as a separate AE on the eCRF. Additionally, the condition that led to a medical or surgical procedure should be recorded as the AE, not the procedure itself.

Any medical condition already present at screening or baseline should not be reported as an AE unless the medical condition or signs or symptoms present at baseline worsens in severity or seriousness at any time during the study. In this case, it should be reported as an AE.

Clinically significant abnormal laboratory or other examination findings that are detected during the study or are present at baseline and significantly worsen during the study should be reported as AEs. The investigator will exercise his or her medical and scientific judgment in deciding whether an abnormal laboratory finding or other abnormal assessment is clinically significant. Significant abnormal laboratory values occurring during the clinical study will be followed until repeat tests return to normal, stabilize, or are no longer clinically significant. Any abnormal test that is determined to be an error does not require reporting as an AE.

Each AE is to be evaluated for duration, severity, seriousness, and causal relationship to the IMP. For each AE, the following information will be recorded:

- Description of the event (eg, headache)
- Date of onset
- Date of resolution (or that the event is continuing)
- Action taken as a result of the event
- Seriousness of the event
- Severity of the event

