11.3. Adverse Events of Special Interest

Adverse events of special interest (AESI) are included in this protocol for reasons either associated with other lipid lowering therapies or where deemed important based on nonclinical data. AESI for this protocol include: metabolic acidosis (clinical laboratories), hypoglycemia, muscular (AE and CK evaluation), hepatic, and neurocognitive/neurologic events.

Muscle: Muscle events have been associated with statins (Thompson 2003) and other lipidlowering therapies and are mentioned in the product information for these therapies. Muscle symptoms through AE review, CK elevations, and symptoms of potential myopathy will be closely monitored.

Hepatic: Hepatic function will be monitored throughout with the clinical safety labs. More detailed investigation will occur if the safety clinical laboratory results are $>3 \times$ ULN.

Neurocognitive Events: Theoretically, it is possible that lipid-lowering agents that disrupt cholesterol homeostasis in the brain could impact neurological function, and there have been reports of cognitive impairment (eg, memory loss) associated with the use of statin drugs

(FDA 2012). Summarization of events will occur using prespecified Medical Dictionary for Regulatory Activities (MedDRA) terms outlined in the statistical analysis plan (SAP).

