Neurocognitive events will be identified and evaluated by routine safety monitoring of PE findings and AEs. Summarization of neurocognitive events will occur using prespecified MedDRA terms and will be performed by SOC and PT, severity, and relationship to study drug.

Clinical Endpoints

Clinical endpoints using standardized definitions will be adjudicated by an independent blinded expert CEC for all ongoing Phase 3 studies in the bempedoic acid program. Investigator-reported clinical endpoints and adjudicated clinical endpoints will be summarized by event type. Additional details regarding the clinical endpoints and their definitions will be included in CEC Charter.

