Muscular disorders	Myoglobin blood present
Muscular disorders	Myoglobin urine present
Muscular disorders	Myoglobinaemia
Muscular disorders	Myoglininuria
Muscular disorders	Myopathy
Muscular disorders	Myopathy toxic
Muscular disorders	Necrotizing myositis
Muscular disorders	Pain in extremity
Muscular disorders	Rhabdomyolysis
Neurocognitive/Neurologic disorders	Amnesia
Neurocognitive/Neurologic disorders	Cognitive disorder
Neurocognitive/Neurologic disorders	Confusional state
Neurocognitive/Neurologic disorders	Disorientation
Neurocognitive/Neurologic disorders	Memory impairment
Neurocognitive/Neurologic disorders	Mental status changes
Renal disorders	Acute kidney injury
Renal disorders	Acute prerenal failure
Renal disorders	Blood creatinine abnormal
Renal disorders	Blood creatinine increased
Renal disorders	Blood urea abnormal
Renal disorders	Blood urea increased
Renal disorders	Blood urea nitrogen/Creatinine ratio increased
Renal disorders	Creatinine renal clearance abnormal
Renal disorders	Creatinine renal clearance decreased
Renal disorders	Glomerular filtration rate abnormal
Renal disorders	Glomerular filtration rate decreased
Renal disorders	Gout
Renal disorders	Oliguria
Renal disorders	Prerenal failure
Renal disorders	Renal failure
Renal disorders	Renal function test abnormal
Renal disorders	Renal impairment

Version 1.2, Dec 05, 2018 Statistical Analysis Plan

	Statistical Analysis Plan
Title: Protocol: Clinical Phase: Product: Version (Date): Status:	A MULTICENTER OPEN-LABEL EXTENSION (OLE) STUDY TO ASSESS THE LONG-TERM SAFETY AND EFFICACY OF BEMPEDOIC ACID (ETC-1002) 180 MG ETC-1002-050 3 ETC-1002 Statistical Analysis Plan – Version 1.2 Final
Prepared by:	
	06 Dec 2018 01:14:051+0000 REASON: I approve this document f1330a26-8e65-4f1e-b28b-172f4186890d
	Date
	06 Dec 2018 01:10:021+0000
	REASON: I approve this document
	17064876-dedd-4660-9752-8d3bc4287a9e
	Date
	06 Dec 2018 05:19:028+0000
	REASON: I approve this document
-	086860ea-c4a5-4e1a-a755-f8a0a04d5e64
	Date
Esperion Theraper	tics
	07 Dec 2018 15:53:016+0000
	REASON: I approve this document
	fdfe4eec-c142-42c7-bf98-459047a30340
	Date
Esperion Theraper	tics
Confidential	Page 1 of 27

Page 53 of 129

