#### 5.4.2 Adverse Events of Special Interest

Adverse events of special interest (AESI) will be identified based on a pre-defined list of preferred terms provided by the sponsor (Appendix 2).

AESI will be presented in a listing and summarized by SOC, PT, and previous treatment group in parent study and overall in OLE study. A separate table for treatment-emergent AESI resulting in the discontinuation of study drug will be summarized by SOC, PT, and previous treatment group in the parent study and overall in OLE study.

In addition to adverse events, AESI is also being evaluated based on safety lab parameters. The details are provided in 5.4.5.

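### The neurocognitive/neurologic AESI rests on six preferred terms with no specific diagnosis and nothing beyond cognition or mental state, so a case recorded as dementia, delirium or encephalopathy falls outside the AESI summaries

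*SAP*

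**What the plan says.** Protocol 11.3 sets out the categories: "AESI for this protocol include: metabolic acidosis (clinical laboratories), hypoglycemia, muscular (AE and CK evaluation), hepatic, and neurocognitive/neurologic events". Its reason for the last one is that disturbing cholesterol balance in the brain "could impact neurological function, and there have been reports of cognitive impairment (eg, memory loss) associated with the use of statin drugs". The choice of MedDRA terms is left to the SAP.

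The current SAP, v1.3, fixes the selection rule in 5.4.2: "Adverse events of special interest (AESI) will be identified based on a pre-defined list of preferred terms provided by the sponsor (Appendix 2"). Section 5.4.2.1 adds a separate neurocognitive summary: "Summarization of neurocognitive events will occur using pre-specified MedDRA terms and will be performed by SOC, severity, and relationship to study drug" (the same sentence stands in v1.2, 5.4.4). The SAP gives no term list other than Appendix 2.

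Under "Neurocognitive/Neurologic disorders", Appendix 2 has six preferred terms: amnesia, cognitive disorder, confusional state, disorientation, memory impairment and mental status changes. The six are the same in v1.1, v1.2 and v1.3.

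Protocol 11.1.3 tells sites how to name an event: wherever possible, "a specific disease or syndrome rather than individual associated signs and symptoms should be identified by the investigator". Several findings with one cause are to be reported as one event. A sign or symptom that the investigator does not regard as part of a disease is recorded separately.

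**The concern.** The recording rule and the term list pull in different directions. A memory complaint that is worked up to dementia, or confusion that is diagnosed as delirium, should be entered under the diagnosis where possible. The list mostly holds symptoms and broad descriptions, so the diagnosed form of the same problem may not be picked up.

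The category is also labelled neurocognitive/neurologic, but no listed term would bring in a motor, sensory or other neurologic event outside cognition or mental state.

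At stake is one grouped safety count in a study whose primary objective is long-term safety. An AESI grouping exists to show how many patients had any event of a given kind. If established diagnoses are outside the grouping, the count can look low because of the choice of terms.

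**Working it through.** The plan states no figure for this AESI, so the check is mainly a comparison of texts.

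**1. Count the terms (Appendix 2, v1.1, v1.2 and v1.3).**
- Terms under the neurocognitive/neurologic label: 6 in each version.
- Dementia, delirium or encephalopathy terms under that label: 0.
- Terms outside cognition or mental state: 0.

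**2. Trace how a case is recorded and selected.**

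| How the investigator records the case | On the list? | In AESI summaries? | In general TEAE tables? |
|---|---|---|---|
| Memory impairment, amnesia, disorientation | Yes | Yes | Yes |
| Cognitive disorder, confusional state | Yes | Yes | Yes |
| Dementia, delirium, encephalopathy | No | No | Yes |
| Motor or sensory neurologic event | No | No | Yes |

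The third row assumes that a reported diagnosis is coded to a preferred term for that diagnosis, and that the patient has no other event under a listed term.

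**3. See which outputs use the list (SAP v1.3).** These are the AESI listing and summary and the table of AESI leading to discontinuation (5.4.2), the AESI subgroup tables (5.4.1) and, since no other list is given, the neurocognitive summary (5.4.2.1). The Day 120 addendum also names exposure-adjusted AESI tables and gives no list of its own.

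**4. Ask whether another route catches the case.** For hepatic, muscle, glucose and renal safety, SAP v1.3, 5.4.4 adds laboratory criteria. The neurocognitive category has none. Section 5.4.2.1 mentions physical examination findings, but under 5.4.5 a qualifying change enters the summaries as an adverse event, so it meets the same list.

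**5. Compare with the other categories.** Elsewhere Appendix 2 mixes findings with diagnoses: myopathy and rhabdomyolysis under muscle, acute kidney injury and renal failure under renal, type 2 diabetes and diabetic ketoacidosis under diabetes. The neurocognitive list has no diagnosis as specific as these.

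**6. Scale per patient.** With the planned N of about 1300 (protocol synopsis and 6.5), one omitted patient changes the AESI incidence by 1/1300 = 0.00077, or 0.077 percentage points. The total would be this figure times the number of omitted patients, which the documents do not allow anyone to estimate.

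**The case against.** The strongest reply is that nothing is lost from the safety report. The primary endpoint is the incidence of all treatment-emergent events. SAP v1.3, 5.4.1 tabulates these by SOC and PT, with separate tables for serious, related, fatal and withdrawal events and listings of all events. A dementia or delirium term would appear there by name. This stands: a reader might infer that diagnosed cases vanish from the analysis, and they do not. What the general tables lack is one row for patients with any neurocognitive event, because such cases are spread over separate terms.

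Second, the recording rule is qualified. A reader might take it as an obligation to enter only diagnoses, but the text says wherever possible and uses should, and it provides for symptoms outside a diagnosis. Cases recorded as cognitive disorder or confusional state are counted. This narrows the gap without closing it.

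Third, a reader might say that half of the named AESI goes unevaluated. The documents do not support that. Protocol 11.3 discusses the category under neurocognitive events and gives memory loss as its example, and amnesia and memory impairment are listed. What remains is a label wider than its content.

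Fourth, protocol 12.6 says this summary "will be performed by SOC and PT, severity, and relationship to study drug", while SAP v1.3, 5.4.2.1 omits PT. A reader might infer that term-level counts are lost, but the AESI table in 5.4.2 is already by SOC and PT.

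Finally, the list was prespecified and has not changed between versions, and a narrow list favours specificity and comparability. That is a fair reason to keep the six terms visible. It does not explain why diagnoses are included in other categories and not in this one.

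**Conclusion.** The point holds in a limited form. Following the plan as written, a patient whose only neurocognitive event is recorded as dementia, delirium or encephalopathy is left out of the AESI, neurocognitive, AESI-discontinuation and AESI-subgroup summaries. The patient is still counted in the primary endpoint and in the general TEAE tables, and in the SAE tables if the event is serious. Non-cognitive neurologic events are outside the AESI altogether, although its label suggests otherwise.

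The direction is known: the AESI count can only be too low from this cause. The size is not. It is tempting to assume a rate of diagnosed cognitive disease and multiply by the planned exposure, but the documents give no rate for diagnosed or listed events. Patients with an earlier listed term are already counted, and exclusion criterion 5 keeps out disorders that interfere with understanding or consent. Only the per-patient figure of about 0.08 percentage points at N = 1300 is firm.

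The conclusion rests on two readings: that the prespecified terms in 5.4.2.1 are those of Appendix 2, and that a diagnosis is coded to its own preferred term. The study is descriptive, with no inference planned, so this is a cheap improvement in ascertainment and does not threaten the main result.

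**What to change.** In Appendix 2 of SAP v1.3:

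- Add diagnosis-level terms to this category: dementia and its subtypes, delirium and encephalopathy.
- In the AESI and neurocognitive summaries, show one row for patients with any listed term, and show the six existing terms as a subset.
- Either add neurologic terms outside cognition, or rename the category neurocognitive and state that only the cognitive part of the protocol's AESI is evaluated.

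No new data are needed. The cost is a longer list and a rerun of existing tables. The widened count is less directly comparable with any study or interim output that used the six terms; the subset rows deal with that.

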### 5.4.5 Laboratory Evaluations

Two sets of baseline for safety parameters are defined, similar to that for the efficacy parameters, baseline from the parent study and the baseline from the OLE study.

Continuous laboratory parameters (serum chemistry, hematology, coagulation (only for those patients receiving anti-coagulation), urinalysis, urinalysis [microscopic]) listed in Table 4 will be summarized using descriptive statistics at each scheduled visit starting from the baseline of the parent study. The similar on-treatment and completer analysis set approach for efficacy analysis described in section 5.3 will be used for safety laboratory analysis. All analysis will use conventional unit and SI unit will be provided for selected parameters.

Fasting serum glucose and HbA1c will be summarized using descriptive statistics for the observed value and the change, percent change from baseline by history of diabetics. Missing values for any of the laboratory evaluations will not be imputed; that is, only observed case data will be used.

Confidential

Page 18 of 27

Page 70 of 129

Version 1.2, Dec 05, 2018 Statistical Analysis Plan

Categorical urinalysis data will be listed, but will not be summarized.

As part of the AESI evaluation, below safety lab abnormality will be summarized by treatment group. All post-baseline lab values during the on-treatment period are being considered. Further details are provided in Section 5.4.6.1 through 5.4.6.4.

- ALT or AST (>  $3 \times$  ULN and > $5 \times$  ULN)
- TB (>  $2 \times ULN$ )
- Potential Hy's Law case: (ALT and/or AST > 3 × ULN with concurrent TB > 2 × ULN)
- CK (>  $5 \times ULN$ ) and (> $10 \times ULN$ )
- Fasting Serum Glucose (mg/dL) ( $\leq$  50, and  $\geq$  126) by history of diabetics
- HbA1C ( $\geq 6.5\%$ ) by history of diabetics
- Creatinine (change from baseline for >1 mg/dL)
- eGFR (< 15 mL/min/1.73m^2, 15 29 mL/min/1.73m^2)
- Hgb (g/dL) (decrease from baseline for  $\geq 2$  g/dL)
- Hgb (< 8 g/dL)

The number and percentage of patients with the following laboratory abnormalities will be summarized by the parent study baseline statin intensity, previous treatment group in the parent study, and overall in the OLE study:

- ALT or AST (>  $3 \times$  ULN and > $5 \times$  ULN)
- TB (>  $2 \times ULN$ )
- Potential Hy's Law case: (ALT and/or AST >  $3 \times$  ULN with concurrent TB >  $2 \times$  ULN)
- CK (>  $5 \times$  ULN) and (> $10 \times$  ULN)
- Creatinine (change from baseline for > 1 mg/dL)
- eGFR (< 15 mL/min/1.73m^2, 15 29 mL/min/1.73m^2)
- Hgb (g/dL) (decrease from baseline for  $\geq 2$  g/dL)
- Hgb (< 8 g/dL)

Confidential

Page 19 of 27

Table 2:	Clinical Laboratory Parameters (Safety)
----------	--

Clinical Laboratory Test	Clinical Laboratory Test				
Hematology	Blood Chemistry (serum, fasting)				
• Hematocrit (Hct)	• Albumin (Alb)				
• Hemoglobin (Hgb)	• Alkaline phosphatase (ALK-P)				
• Mean corpuscular hemoglobin (MCH)	• Alanine aminotransferase (ALT; SGPT)				
• Mean corpuscular hemoglobin	• Aspartate aminotransferase (AST;				
concentration (MCHC)	SGOT)				
• Mean corpuscular volume (MCV)	• Blood urea nitrogen (BUN)				
• Platelet count	• Calcium (Ca)				
• Red blood (RBC) cell count	• Carbon dioxide (CO2)				
• White blood (WBC) cell count with	• Chloride (Cl)				
differential (absolute and %)	• Creatinine				
Urinalysis (Dipstick)	• Creatine kinase (CK)				
• Clarity	• Glucose				
• Bilirubin	• Lactate dehydrogenase (LDH)				
• Color	Phosphorus				
• Glucose	• Potassium (K)				
• Ketones	• Sodium (Na)				
• Leukocyte esterase	• Total and direct bilirubin (TB)a				
• Nitrate	• Total protein				
Occult blood	Uric acid				
• pH	Coagulation—only in patients receiving				
• Protein	anticoagulant therapy that in the investigator's				
Specific gravity	judgment require monitoring at Month 0 and				
• Urobilinogen	3 to 5 days post-Month 0				
	• Prothrombin time (PT)				
	• International normalized ration (INR)				
Urinalysis (Microscopic)-only if urine dipstick	Other Labs:				
abnormal	Urine pregnancy test				
• Bacteria	• Hemoglobin A 1C (HbA 1C )				
• Casts					
• Crystals					
• Epithelial cells					
• RBC					
• WBC					

 $^{\rm a}\,$  If TB  ${\geq}1.2 \times$  ULN, a reflex indirect (unconjugated) bilirubin will be obtained.

## Confidential
The number and percentage of patients with laboratory abnormalities (i.e., laboratory values outside the stated laboratory normal range) will be summarized at each time point (i.e., including baseline and post-baseline time points) for each laboratory parameter. The determination of laboratory abnormalities will take into account any unscheduled laboratory assessments. Additional lab-related summaries will be provided as follows for hepatic safety, musculoskeletal safety, diabetes and glycemia, and renal safety.

#### 5.4.5.1 Hepatic Safety

For liver-associated enzymes and total bilirubin (TB), the number and percent of patients with abnormal values for ALT (>3 × ULN, > 5 × ULN), AST (> 3 × ULN, > 5 × ULN), and TB (> 2×ULN) will be summarized by overall, normal baseline ALT/AST/TB and abnormal baseline ALT/AST/TB.

Hy's law criteria (>  $3 \times$  upper limit of normal [ULN] for either ALT or AST, with accompanying TB >  $2 \times$  ULN) will also be applied to the data; any potential Hy's law cases will be listed separately. In the case of patients with Gilbert's disease, TB will be fractionated and the determination of  $2 \times$  ULN will be based upon direct (conjugated) bilirubin.

The number and percentage of patients experiencing a single incident or confirmed and repeated incidence of abnormal liver function test values for ALT (>3 × ULN, >5 × ULN), AST (>3 × ULN, >5 x ULN), CK (>5 × ULN, >10 × ULN) and either ALT and/or AST (>3 × ULN, >5 × ULN) will be summarized by the previous treatment group in the parent study and overall in the OLE study. A single incident is defined as the patient experiencing only one abnormal incident of the liver function test value. Repeated and confirmed incidence is defined as the patient experiencing at least one of the following: the last on-study liver function test value is abnormal, the last on-treatment liver function test value is abnormal liver function test value is followed by another abnormal liver function test value for the same test.

A separate listing for direct TB will be provided for those who have Gilbert's syndrome.

